3.2 Secondary Objective(s), Hypothesis(es), and Endpoint(s)

(1) **Objective**: To evaluate the objective response rate resulting from treatment with Lenvatinib + pembrolizumab.

Hypothesis: Treatment with Lenvatinib + pembrolizumab will result in an improved objective response rate as compared with previously reported therapies including pembrolizumab monotherapy, ipilimumab + nivolumab and tebentafusp.

Secondary Endpoint: Objective response rate (complete and partial responses assessed by iRECIST)

(2) **Objective**: To evaluate the effect of treatment with Lenvatinib + pembrolizumab on overall survival.

Hypothesis: Treatment with Lenvatinib + pembrolizumab will result in improved overall survival as compared with previously reported therapies including pembrolizumab monotherapy, ipilimumab + nivolumab and tebentafusp.

Secondary Endpoint: Overall survival, defined as the time from enrollment to death (resulting from any cause).

(3) **Objective**: To evaluate the safety and tolerability of treatment with Lenvatinib + pembrolizumab in patients with metastatic uveal melanoma.

Hypothesis: Treatment with Lenvatinib + pembrolizumab will demonstrate an acceptable toxicity profile in patients with metastatic uveal melanoma.

Secondary Endpoint:

• Adverse events (per CTCAE v5.0)

• Frequency of treatment interruption, dose reduction, and treatment discontinuation due to treatment related adverse events (TRAE).

3.3 Exploratory Objective(s)

(1) **Objective:**

To evaluate correlative biomarkers from tumor and blood specimens in patients treated with Lenvatinib + pembrolizumab.

Hypothesis: Treatment with Lenvatinib + pembrolizumab will result in changes in the tumor infiltrating immune cell profile and tumor gene expression profile.

Secondary Endpoint:

- Multiplex immunohistochemical analysis of tumor biopsy specimens for characterization of the tumor immune profile.
- Gene expression profiling of tumor biopsy specimens by RNAseq.

4.0 BACKGROUND & RATIONALE

4.1 Background

Uveal melanoma

Metastatic uveal melanoma is associated with a very poor prognosis with median survival of 6-12 months [1]. Unfortunately, systemic therapy with immune checkpoint inhibitors has demonstrated inadequate efficacy. In a phase II clinical trial with ipilimumab, no objective responses were observed and the median progression free survival (PFS) was 2.8 months [2]. A small phase II clinical trial (17 patients) evaluated the efficacy of pembrolizumab monotherapy. Two out of the 17 patients had an objective response (11.7%) and median PFS was 3.8 months [3]. Treatment with the combination of ipilimumab + nivolumab was evaluated in a phase II clinical trial that showed an objective response rate (ORR) of 18% with median PFS of 5.5 months and median overall survival of 19.1 months [4]. The results of the phase III clinical trial evaluating the bispecific fusion protein Tebentafusp in patients with metastatic uveal melanoma were reported at the 2021 AACR annual meeting. In this clinical trial, patients were randomly assigned (2:1) to either treatment with tebentafusp or investigator choice of therapy (pembrolizumab, ipilimumab or dacarbazine). The authors reported a median overall survival of almost 22 months for tebentafusp compared with 16 months in the investigator choice arm. Tebentafusp resulted in an ORR of 9% [5]. As such, effective therapies for patients with metastatic uveal melanoma represents a significant unmet clinical need.

Pembrolizumab is a potent humanized immunoglobulin G4 (IgG4) monoclonal antibody (mAb) with high specificity of binding to the programmed cell death 1 (PD-1) receptor, thus inhibiting its interaction with programmed cell death ligand 1 (PD-L1) and programmed cell death ligand 2 (PD-

L2). Based on preclinical in vitro data, pembrolizumab has high affinity and potent receptor blocking activity for PD-1. Pembrolizumab has an acceptable preclinical safety profile and is in clinical development as an intravenous (IV) immunotherapy for advanced malignancies. Keytruda[®] (pembrolizumab) is indicated for the treatment of patients across a number of indications because of its mechanism of action to bind the PD-1 receptor on the T cell. For more details on specific indications refer to the Investigator brochure (IB).

Lenvatinib (E7080 or MK-7902) is a potent small molecule inhibitor of multiple kinases including vascular endothelial growth factor receptors (VEGFR) 1-3, fibroblast growth factor receptors (FGFR) 1-4, platelet derived growth factor receptor alpha (PDGFR α), KIT and RET. Several of these kinases are overexpressed by various cancers and contribute to tumor proliferation, invasion, metastasis and immune suppression in the tumor microenvironment [6].

4.1.1 Pharmaceutical and Therapeutic Background

The importance of intact immune surveillance function in controlling outgrowth of neoplastic transformations has been known for decades [Disis, 2010]. Accumulating evidence shows a correlation between tumor-infiltrating lymphocytes in cancer tissue and favorable prognosis in various malignancies. In particular, the presence of CD8+ T-cells and the ratio of CD8+ effector Tcells/FoxP3+ regulatory T-cells (T-regs) correlates with improved prognosis and long-term survival in solid malignancies, such as ovarian, colorectal, and pancreatic cancer; hepatocellular carcinoma; malignant melanoma; and renal cell carcinoma. Tumor-infiltrating lymphocytes can be expanded ex vivo and reinfused, inducing durable objective tumor responses in cancers such as melanoma [Dudley et al., 2005; Hunder et al., 2008].

The PD-1 receptor-ligand interaction is a major pathway hijacked by tumors to suppress immune control. The normal function of PD-1, expressed on the cell surface of activated T-cells under healthy conditions, is to down-modulate unwanted or excessive immune responses, including autoimmune reactions. PD-1 (encoded by the gene *Pdcd1*) is an immunoglobulin (Ig) superfamily member related to cluster of differentiation 28 (CD28) and cytotoxic T-lymphocyte-associated protein 4 (CTLA-4) that has been shown to negatively regulate antigen receptor signaling upon engagement of its ligands (PD-L1 and/or PD-L2) [Greenwald et al., 2005; Okazaki et al., 2001].

The structure of murine PD-1 has been resolved [Zhang et al., 2004]. PD-1 and its family members are type I transmembrane glycoproteins containing an Ig-variable–type (IgV-type) domain responsible for ligand binding and a cytoplasmic tail responsible for the binding of signaling molecules. The cytoplasmic tail of PD-1 contains 2 tyrosine-based signaling motifs, an immunoreceptor tyrosine-based inhibition motif, and an immunoreceptor tyrosine-based switch motif. Following T-cell stimulation, PD-1 recruits the tyrosine phosphatases, SHP-1 and SHP-2, to the immunoreceptor tyrosine-based switch motif within its cytoplasmic tail, leading to the dephosphorylation of effector molecules such as CD3 zeta (CD3 ζ), protein kinase C-theta (PKC θ), and zeta-chain-associated protein kinase (ZAP70), which are involved in the CD3 T-cell signaling cascade [Okazaki et al., 2001; Chemnitz et al., 2004; Sheppard et al., 2004; and Riley, 2009]. The mechanism by which PD-1 down-modulates T-cell responses is similar to, but distinct from, that of CTLA-4, because both molecules

regulate an overlapping set of signaling proteins [Parry et al., 2005; Francisco, 2010]. As a consequence, the PD-1/PD-L1 pathway is an attractive target for therapeutic intervention in metastatic immune checkpoint inhibitor naïve uveal melanoma.

4.1.2 Lenvatinib

VEGF signaling within the tumor microenvironment contributes to tumor proliferation, angiogenesis, and exerts multiple immune suppressive effects which disrupt anti-tumor immunity. Specifically, high levels of VEGF within the tumor microenvironment is associated with increased tumor infiltration of regulatory T cells (Treg). Additionally, VEGF signaling in activated T cells results in increased expression of multiple inhibitory immune receptors including PD-1, CTLA-4, TIM-3 and LAG-3 [18].

Lenvatinib has demonstrated potent antiangiogenic and antiproliferative activity in preclinical models. In a syngeneic mouse tumor model, treatment with Lenvatinib resulted in increased tumor infiltration of activated CD8+ T cells (expressing granzyme B and IFN- γ) and plasmacytoid dendritic cells and decreased the number of tumor associated macrophages (TAM) [19]. Lenvatinib has also resulted in decreased tumor infiltration of Tregs in patients with advanced renal cell carcinoma [20].

4.1.3 Lenvatinib + Pembrolizumab

Multiple factors contribute to tumor immune evasion which include impaired T cell priming and activation by antigen presenting cells, impaired T cell trafficking into tumors, exhaustion of tumorspecific T cells, immunosuppressive cytokines (TGF β , IL-10, etc.), and others [21]. Due to the immunosuppressive roles of VEGF and PD-1 signaling in tumors, pre-clinical testing was done to evaluate the effect of Lenvatinib + pembrolizumab in syngeneic mouse tumor models. Using the CT26 CRC and Hepa1-6 HCC mouse tumor models, Lenvatinib + pembrolizumab resulted in improved anti-tumor activity than either agent alone [22]. Based on the mechanistic rationale and encouraging pre-clinical data, the Study 111/Keynote-146 was designed to evaluate the safety, tolerability and efficacy of the combination of Lenvatinib + pembrolizumab in patients with advanced solid tumors. This clinical trial showed that Lenvatinib 20 mg/day + pembrolizumab 200 mg IV every 3 weeks exhibited an acceptable safety profile and significant preliminary anti-tumor efficacy. Subsequent clinical trials in patients with advanced endometrial carcinoma and renal cell carcinoma confirmed excellent anti-tumor activity. These results led to the FDA approval of Lenvatinib + Pembrolizumab for patients with metastatic endometrial cancer and metastatic renal cell carcinoma [23].

4.1.4 Preclinical and Clinical Trial Data

Refer to the Investigator's Brochure for Preclinical and Clinical data.

4.2 Rationale

4.2.1 Rationale for the Trial and Selected Population

The combination of Lenvatinib + pembrolizumab has demonstrated excellent clinical efficacy in patients with metastatic endometrial cancer as well as metastatic renal cell carcinoma. Of note, it appears that the combination of these drugs may result in a synergistic therapeutic effect rather than merely an additive benefit. Consequently, this combination is now being evaluated across a broad range of advanced solid tumors.

Uveal melanomas express high levels of the immunosuppressive molecules VEGF and FGF [24]. Consequently, targeting VEGF and FGF signaling pathways in the tumor microenvironment represents an attractive approach to decrease the local immunosuppression. The anticipated effect of blockade of both VEGF and PD-1 signaling will be to modulate the tumor microenvironment by increasing tumor infiltration of CD8+ T cells, decreasing intratumoral Tregs and TAMs and reinvigorating exhausted tumor-specific CD8+ T cells. It is noteworthy that high numbers of Tregs in uveal melanoma metastases has been correlated with poor response to immune checkpoint inhibitors [25]. As such, the capacity of Lenvatinib to decrease the number of tumor infiltrating Tregs may represent a significant mechanism of enhancing anti-tumor immunity when used in combination with pembrolizumab.

4.2.2 Justification for Dose

The planned dose of pembrolizumab for this study is 200 mg every 3 weeks (Q3W). Based on the totality of data generated in the Keytruda development program, 200 mg Q3W is the appropriate dose of pembrolizumab for adults across all indications and regardless of tumor type. As outlined below, this dose is justified by:

- Clinical data from 8 randomized studies in melanoma and NSCLC indications demonstrating flat dose- and exposure-efficacy relationships from 2 mg/kg Q3W to 10 mg/kg Q2W, representing an approximate 5- to 7.5-fold exposure range (refer to IB, Section 5.2.2)
- Population PK analysis showing that both fixed dosing and weight-based dosing provides similar control of PK variability with considerable overlap in the distributions of exposures, supporting suitability of 200 mg Q3W
- Clinical data showing meaningful improvement in benefit-risk including overall survival at 200 mg Q3W across multiple indications, and
- Pharmacology data showing full target saturation in both systemic circulation (inferred from pharmacokinetic [PK] data) and tumor (inferred from physiologically-based PK [PBPK] analysis) at 200 mg Q3W

The dose for Lenvatinib in this clinical trial will be 20 mg daily. This dose of Lenvatinib has been shown to be safe and well tolerated by several clinical trials using this combination [26]. The combination of Lenvatinib 20 mg PO daily with Pembrolizumab 200 mg IV every 3 weeks has been approved by the

FDA for treatment of patients with metastatic renal cell carcinoma and metastatic endometrial carcinoma that is not microsatellite instability-high or mismatch repair deficient (see Lenvatinib package insert).

4.2.2.1 Planned Exploratory Biomarker Research

Paired fresh tumor biopsy specimens will be collected (pre-treatment and cycle 3 day 8) from at least 15 subjects (in no certain order). Subjects with tumor metastases that are not amenable to image guided biopsies or who have a contraindication to biopsy (such as anticoagulation therapy that cannot be interrupted for a biopsy) are still eligible for participation in the clinical trial without the biopsies. Archival tissue may be used in place of pre-treatment biopsy. These specimens will be banked for biomarker analysis that will include tumor immune cell profiling and gene expression analysis. Biomarker analysis will be performed for evaluation of predictive and/or prognostic biomarkers of tumor response and survival.

5.0 METHODOLOGY

5.1 Study Population

5.1.1 Participant Inclusion Criteria

Participants are eligible to be included in the study only if all of the following criteria apply:

- 1. Male/female participants who are at least 18 years of age on the day of signing informed consent with histologically confirmed diagnosis of uveal melanoma that is unresectable or metastatic will be enrolled in this study.
- 2. Male participants:

A male participant must agree to use a contraception as detailed in Appendix 3 of this protocol during the treatment period and for at least 120 days after the last dose of Lenvatinib and refrain from donating sperm during this period.

3. Female participants:

A female participant is eligible to participate if she is not pregnant (see Appendix 3), not breastfeeding, and at least one of the following conditions applies:

a. Not a woman of childbearing potential (WOCBP) as defined in Appendix 3 OR

b. A WOCBP who agrees to follow the contraceptive guidance in Appendix 3 during the treatment period and for at least 120 days post pembrolizumab or post Lenvatinib whichever occurs last.

4. The participant (or legally acceptable representative if applicable) provides written informed consent for the trial.

- 5. Have measurable disease based on iRECIST. Lesions situated in a previously irradiated area are considered measurable if progression has been demonstrated in such lesions.
- 6. Have provided archival tumor tissue sample or newly obtained core or excisional biopsy of a tumor lesion not previously irradiated. Formalin-fixed, paraffin embedded (FFPE) tissue blocks are preferred to slides. If slides are only available, ten slides would be required. Newly obtained biopsies are preferred to archived tissue.
- 7. Have an Eastern Cooperative Oncology Group (ECOG) performance status of 0 to 1. Evaluation of ECOG is to be performed within 7 days prior to the first dose of study intervention.
- 8. Have adequate organ function as defined in the following table (Table 2). Specimens must be collected within 7 days prior to the start of study intervention.
- 9. Paired fresh tumor biopsy specimens (to be collected pre- treatment and cycle 3 day 8) will be collected for at least 15 patients (in no certain order) who consent. Subjects with tumor metastases that are not amenable to image guided biopsies or who have a contraindication to biopsy (including but not limited to anticoagulation therapy that cannot be interrupted for a biopsy) are still eligible for participation in the clinical trial without undergoing biopsies. Archival tissue may be used in place of pre-treatment biopsy.

System	Laboratory Value			
Hematological				
Absolute neutrophil count (ANC)	≥1500/µL			
Platelets	≥100 000/µL			
Hemoglobin	\geq 9.0 g/dL or \geq 5.6 mmol/L ^a			
Renal				
Creatinine OR Measured or calculated ^b creatinine clearance (GFR can also be used in place of creatinine or CrCl)	$\leq 1.5 \times \text{ULN } \underline{\text{OR}}$ $\geq 30 \text{ mL/min for participant with creatinine levels}$ $> 1.5 \times \text{institutional ULN}$			
Hepatic				
Total bilirubin	\leq 1.5 ×ULN OR direct bilirubin \leq ULN for participants with total bilirubin levels >1.5 × ULN (patients with clinical evidence of Gilbert's syndrome and elevated bilirubin are eligible for participation).			
AST (SGOT) and ALT (SGPT)	\leq 2.5 × ULN (\leq 5 × ULN for participants with liver metastases)			

Table 2 Adequate Organ Function Laboratory Values

Coagulation					
International normalized ratio (INR) OR prothrombin time (PT) Activated partial thromboplastin time (aPTT)	\leq 1.5 × ULN unless participant is receiving anticoagulant therapy as long as PT or aPTT is within therapeutic range of intended use of anticoagulants				
ALT (SGPT)=alanine aminotransferase (serum glutamic pyruvic transaminase); AST (SGOT)=aspartate aminotransferase (serum glutamic oxaloacetic transaminase); GFR=glomerular filtration rate; ULN=upper limit of normal.					
^a Criteria must be met without erythropoietin dependency and without packed red blood cell (pRBC) transfusion within last 2 weeks.					
^b Creatinine clearance (CrCl) should be calculated per	institutional standard.				
Note: This table includes eligibility-defining laboratory value requirements for treatment; laboratory value requirements should be adapted according to local regulations and guidelines for the administration of specific chemotherapies.					

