1.0 TRIAL SUMMARY

Abbreviated Title	Lenvatinib plus pembrolizumab in patients with immune checkpoint inhibitor naïve metastatic uveal melanoma
Trial Phase	Phase II
Clinical Indication	Treatment of participants with immune checkpoint inhibitor naïve metastatic uveal melanoma
Trial Type	Interventional
Type of control	n/a
Route of administration	Oral and IV
Treatment Groups	Single arm: Lenvatinib 20 mg daily plus pembrolizumab 200 mg IV every 3 weeks.
Number of trial participants	30
Estimated enrollment period	20 months
Estimated duration of trial	48 months (FPFV to LPLV)
Duration of Participation	Subjects will participate in the clinical trial from the time of signing the ICF until the final protocol specified contact. Subjects who discontinue treatment for reasons other than disease progression or treatment related toxicity will have post-treatment follow-up until documented radiographic evidence of disease progression (per iRECIST), initiation of a subsequent anti-cancer therapy, death, pregnancy, withdrawal of consent, lost to follow up or the end of the clinical trial.
Estimated average length of treatment per patient	6 months

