12-lead ECG with QTcF Determination (Single)		X	x			х					X	X	X	Х			Every 4 cycles. ECG at Screening, C1D1, C2D1, D1of every fourth cycle (12 weeks) thereafter (e.g., C6, C10, C14, etc.), EOT, and safety follow-up. For high-risk participants (Section 6.1.2.7), conduct ECG monitoring every cycle. If Lenvatinib is discontinued, ECGs are only required at the EOT and Safety Follow-up visits.

Study Pariod:	Scra	aning			T	ntarria	ntion	(21 D	ov Cv	alec)				Post t	eatment Visits		Notes
Study I eriod.	5010	ennig					mion	(21-D	ay Cy		C6		End of	1 05t ti			INDIES
Visit Number/Title:	1/Scr	ening		C1		C	r7	C3	C4	C5	to C25	≥ C36	Treatment	Safety Fallow	Efficacy	Survival	
Cycle Day	1/501	coning	1	8	15	1	15	1	1	1	1	1		up	ronow-up	10	
Scheduling Window (days)	-42 to - 1	-28 to - 1	±3	±3	±3	±3	±3	±3	±3	±3	±3	±3	At time of treatment discontin uation	Approx. 30d after last dose (± 7d)	Q6W (Y1) or Q9W (Y2+) (± 7d)	Q12W ^a (± 14d)	
MUGA Scan or ECHO		х												Х			Additional LVEF assessments may be performed as clinically indicated.
ECOG Performance Status		X*	X			X		х	х	X	Х	Х	Х	Х			Performance status obtained on C1D1 may also be used as the screening value to determine eligibility. *Screening ECOG within 7 days before initiation of study intervention. If performed within 7 days prior to day one ECOG does not need to be repeated on Day 1
Laboratory Procedure	s/Asses	sments	(Loca	ıl Lat	orate	ory)			1	1	1	1		1	I		
Serum β-hCG Pregnancy Test (WOCBP only)		х				X		X	X	X	х	Х	Х	X			WOCBP require a negative test. If more than 24 hours have elapsed before the first dose of study intervention, another pregnancy test is required. A serum pregnancy test will be performed per Appendix 2.

Study Period:	Scree	ening			I	nterve	ntion	(21-D	ay Cy	cles)				Post ti	eatment Visits	5	Notes
Visit Number/Title:	1/Scre	Screening		C1		0	22	C3	C4	C5	C6 to C35	≥ C36	End of Treatment	Safety Follow-up	Efficacy Follow-up	Survival FU	
Cycle Day			1	8	15	1	15	1	1	1	1	1		-	-		
Scheduling Window (days)	-42 to - 1	-28 to - 1	±3	±3	±3	±3	±3	±3	±3	±3	±3	±3	At time of treatment discontin uation	Approx. 30d after last dose (± 7d)	Q6W (Y1) or Q9W (Y2+) (± 7d)	Q12W ^a (± 14d)	
Serum FSH (WONCBP only)		Х															In the absence of 12 months of amenorrhea, confirmation with 2 FSH measurements in postmenopausal range is required.
HIV, Hepatitis B, and Hepatitis C		X*															*Required at Screening only if mandated by local health authority

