Hematology		X*	х		х	х		х	x	x	Х	Х	Х	Х			Labs obtained on C1D1 may also be used as the screening value to determine eligibility.
Chemistry		X*	х		х	x		х	х	х	Х	Х	Х	х			*Perform screening laboratory tests within 7 days before the first dose. If performed within 7 days prior to day one CMP does not need to be repeated on Day 1
Thyroid Function Tests (LDH, Free T4, TSH)		X*	x			x			x		x	X		X			Labs obtained on C1D1 may also be used as the screening value to determine eligibility. *Perform screening laboratory tests within 7 days before first dose, then at C2 and every 2 cycles thereafter (C4, C6, etc.) If performed within 7 days prior to day one thyroid function and LDH does not need to be repeated on Day 1

Confidential

Study Period:	Scree	ening		Intervention (21-Day Cycles)				Post t	reatment Visit	S	Notes						
Visit Number/Title: Cycle Day	1/Scro	eening	1	C1 8	15	C	2 15	C3	C4	C5	C6 to C35 1	\geq C36	End of Treatment	Safety Follow- up	Efficacy Follow-up	Survival FU	
Scheduling Window (days)	-42 to - 1	-28 to - 1	±3	±3	±3	±3	±3	±3	±3	±3	±3	±3	At time of treatment discontin uation	Approx. 30d after last dose (± 7d)	Q6W (Y1) or Q9W (Y2+) (± 7d)	Q12W ^a (± 14d)	
Urine Dipstick Testing		X*	x		x	X	x	x	x	X	x	x	х				After C1, collect samples at C1D15 and C2 D15 and up to 3 days before D1 of each cycle. If lenvatinib is discontinued, urine dipstick testing no longer required. Urine dipstick testing (or urinalysis) obtained and reviewed on C1D1 may also be used as the screening value to determine eligibility. If 24-hour urine collection for quantitative assessment of proteinuria is required, C1D1 is postponed to after proteinuria result available. *Perform screening urinalysis tests within 7 days before the first dose. If performed within 7 days prior to day one urine dipstick does not need to be repeated on Day 1

Study Period:	Scree	ening			I	nterve	ntion	(21 - D	ay Cy	cles)	1		Endof	Post tr	eatment Visi	its	Notes
Visit Number/Title: Cycle Day	1/Scre	eening	1	C1 8	15	C	2	C3	C4	C5	C6 to C35 1	≥ C36	Treatment	Safety Follow-up	Efficacy Follow- up	Survival FU	
Scheduling Window (days)	-42 to - 1	-28 to - 1	±3	±3	±3	±3	±3	±3	±3	±3	±3	±3	At time of treatment discontin uation	Approx. 30d after last dose (± 7d)	Q6W (Y1) or Q9W (Y2+) (±7d)	Q12W ^a (± 14d)	

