- 9. Has active autoimmune disease that has required systemic treatment in the past 2 years (i.e. with use of disease modifying agents, corticosteroids or immunosuppressive drugs). Replacement therapy (e.g., thyroxine, insulin, or physiologic corticosteroid replacement therapy for adrenal or pituitary insufficiency, etc.) is not considered a form of systemic treatment and is allowed.
- 10. Has a history of (non-infectious) pneumonitis/interstitial lung disease that required steroids or has current pneumonitis/interstitial lung disease.
- 11. Has an active infection requiring systemic therapy.
- 12. Has a history or current evidence of any condition, therapy, or laboratory abnormality that might confound the results of the study, interfere with the participant's participation for the full duration of the study, or is not in the best interest of the participant to participate, in the opinion of the treating investigator.
- 13. Has known psychiatric or substance abuse disorders that would interfere with cooperation with the requirements of the trial.
- 14. Is pregnant or breastfeeding or expecting to conceive or father children within the projected duration of the study, starting with the screening visit through 120 days after the last dose of trial treatment.
- 15. Has had an allogenic tissue/solid organ transplant.
- 16. Uncontrolled blood pressure (Systolic BP>140 mmHg or diastolic BP >90 mmHg) in spite of an optimized regimen of antihypertensive medication.
- 17. Significant cardiovascular impairment: history of congestive heart failure greater than New York Heart Association (NYHA) Class II, unstable angina, myocardial infarction or stroke within 6 months of the first dose of study drug, or cardiac arrhythmia requiring medical treatment at Screening.
- 18. Bleeding or thrombotic disorders or subjects at risk for severe hemorrhage. The degree of tumor invasion/infiltration of major blood vessels (e.g. carotid artery) should be considered because of the potential risk of severe hemorrhage associated with tumor shrinkage/necrosis following lenvatinib therapy.

- 19. Subjects having $\geq 2+$ proteinuria on urine dipstick testing. However, subjects with $\geq 2+$ proteinuria on urine dipstick testing may undergo a 24-hour urine collection for quantitative assessment of proteinuria. Subjects with <1 g/24-hour proteinuria are eligible for participation.

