5.1.3.2 Contraception

Pembrolizumab and lenvatinib may have adverse effects on a fetus in utero. Refer to Appendix 3 for approved methods of contraception.

For this study, male participants will be considered to be of non-reproductive potential if they have azoospermia (whether due to having had a vasectomy or due to an underlying medical condition).

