When study interventions are administered in combination, attribution of an adverse event to a single component is likely to be difficult. Therefore, while the investigator may attribute a toxicity event to lenvatinib or to pembrolizumab alone, both interventions must be held according to the criteria in Table 4 Dose Modification and Toxicity Management Guidelines for Immune-Related Adverse Events Associated with Pembrolizumab.

Holding Study Interventions:

When study interventions are administered in combination, if the AE is considered immune-related, both interventions should be held according to recommended dose modifications.

Restarting Study Interventions:

Participants may not have any dose modifications (no change in dose or schedule) of pembrolizumab in this study, as described in Table 4.

- If the toxicity does not resolve or the criteria for resuming treatment are not met, the participant must be discontinued from all study interventions.
- If the toxicities do resolve and conditions are aligned with what is defined in Table 4, the combination of lenvatinib and pembrolizumab may be restarted at the discretion of the investigator. In these cases where the toxicity is attributed to the combination or to lenvatinib alone, re-initiation of pembrolizumab as a monotherapy may be considered at the principal investigator's discretion.

Table 4 Dose modification and toxicity management guidelines for immune-related AEs associated with pembrolizumab monotherapy and Immunotherapy (IO) Combinations

General instructions:

- 1. Severe and life-threatening irAEs should be treated with IV corticosteroids followed by oral steroids. Other immunosuppressive treatment should begin if the irAEs are not controlled by corticosteroids.
- 2. Study intervention must be permanently discontinued if the irAE does not resolve or the corticosteroid dose is not ≤ 10 mg/day within 12 weeks of the last study intervention treatment.
- 3. The corticosteroid taper should begin when the irAE is \leq Grade 1 and continue at least 4 weeks.
- 4. If study intervention has been withheld, study intervention may resume after the irAE decreased to \leq Grade 1 after corticosteroid taper.

irAEs	Toxicity Grade (CTCAE v5.0)	Action With Pembrolizumab	Corticosteroid and/or Other Therapies	Monitoring and Follow-up		

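### Men's contraception and sperm-donation period is counted from the last lenvatinib dose only, so a man who finishes on pembrolizumab alone has a shortened post-treatment period, or none

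*Combined protocol and SAP*

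**What the plan says.** Three eligibility criteria set a 120-day period, and they do not share a starting point.

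- **Inclusion 2 (men), Section 5.1.1:** contraception in the treatment period, then "for at least 120 days after the last dose of Lenvatinib and refrain from donating sperm during this period".
- **Inclusion 3b (women of childbearing potential), Section 5.1.1:** contraception during the treatment period and "for at least 120 days post pembrolizumab or post Lenvatinib whichever occurs last".
- **Exclusion 14 (both sexes), Section 5.1.2:** excludes people who anticipate a pregnancy; the part that covers men reads "father children within the projected duration of the study, starting with the screening visit through 120 days after the last dose of trial treatment".

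The protocol also provides for lenvatinib stopping first. Under the restarting rules in Section 5.2, when a toxicity is attributed to lenvatinib or to the combination, "re-initiation of pembrolizumab as a monotherapy may be considered at the principal investigator's discretion". Two notes in the Schedule of Activities (Section 2.3) cover the time after lenvatinib stops: "If Lenvatinib is discontinued, ECGs are only required at the EOT and Safety Follow-up visits", and "If lenvatinib is discontinued, urine dipstick testing no longer required".

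On the reason for the precaution, Section 5.1.3.2 names both drugs: "Pembrolizumab and lenvatinib may have adverse effects on a fetus in utero". It sets no time frame and refers to Appendix 3. Appendix 3 sends men to a Section 5.11, evidently 5.1.1, and so back to inclusion 2.

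**The concern.** Once lenvatinib has stopped and pembrolizumab continues, inclusion 2 runs its clock from the drug already withdrawn. The section on overlapping toxicities describes lenvatinib as having a relatively short half-life (28 hours) and pembrolizumab a long one, so the drug left out is the longer-lived of the two.

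At stake is a clear instruction to participants. A man who ends on pembrolizumab alone could, on a correct reading of inclusion 2, be told that he may stop contraception or donate sperm while the 120-day window in exclusion 14 is still open. Exclusion 14 does not fill the gap: it tests what a man expects at entry, imposes no contraception afterwards, and says nothing about sperm donation. Sample size, endpoints and analysis are not touched.

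**Working it through.** **Inputs**

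- 120-day periods and their starting points: inclusion 2 and 3b (Section 5.1.1), exclusion 14 (Section 5.1.2).
- Pembrolizumab on day 1 of each 21-day cycle, for at most 2 years: Table 3, Section 5.2.
- "Estimated average length of treatment per patient": 6 months (Section 1.0), taken here as 182 days.
- Day of the last lenvatinib dose in the examples: day 84. This is an assumption; the protocol gives no such figure.

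**Formula**

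Let L be the day of the last lenvatinib dose, P the day of the last pembrolizumab dose, and g = P − L > 0. The term treatment period is not defined. I take it to include dosing with pembrolizumab alone, the reading most favourable to the protocol. Inclusion 2 then binds until max(P, L + 120), so the days remaining after the last trial dose are

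tail = max(0, 120 − g).

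Counting from the later drug (3b) or from the last trial dose (exclusion 14) ends at P + 120, a tail of 120 for any g.

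| Gap g (days) | Tail, inclusion 2 | Tail, 3b or exclusion 14 anchor |
|---|---|---|
| 0 | 120 | 120 |
| 21 | 120 − 21 = 99 | 120 |
| 42 | 120 − 42 = 78 | 120 |
| 63 | 120 − 63 = 57 | 120 |
| 84 | 120 − 84 = 36 | 120 |
| 105 | 120 − 105 = 15 | 120 |
| 120 or more | 0 | 120 |

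**Treatment of average length**

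- Last pembrolizumab dose within 182 days: cycle 9 day 1 = 8 × 21 + 1 = day 169 (cycle 10 day 1 = 9 × 21 + 1 = day 190, too late).
- Inclusion 2 ends on day 84 + 120 = 204, so the tail is 204 − 169 = 35 days.
- The exclusion 14 date is day 169 + 120 = 289, so the shortfall is 289 − 204 = 85 days.
- For the tail to vanish, lenvatinib must have ended by day 169 − 120 = 49.

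**Longer treatment, same lenvatinib stop**

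- Last pembrolizumab dose at cycle 12 day 1 = 11 × 21 + 1 = day 232.
- g = 232 − 84 = 148, which exceeds 120, so the tail is 0.
- The exclusion 14 date is day 232 + 120 = 352.

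**Does another provision close the gap?**

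- Note b to Table 10 (Appendix 3) has a 120-day period after the last study treatment. It applies only to added condoms where the study drugs may weaken hormonal contraception, and it does not cover sperm donation.
- Pregnancy reporting (Section 6.2.1) runs 120 days from the end of study intervention, or 30 days if new anticancer therapy starts. It detects pregnancies; it does not prevent them.

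**The case against.** The strongest reply is that lenvatinib is planned to end last. Table 3 sets no limit on its duration but caps pembrolizumab at 2 years, and the Schedule of Activities continues lenvatinib dispensing from cycle 36 without pembrolizumab. A man on that path, or one who stops both drugs together, has his full 120 days. This stands, and it confines the problem to men who stop lenvatinib first. It does not remove the problem, because the protocol expressly allows that course.

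Second, the lenvatinib-only anchor may be deliberate. Criteria 2 and 3b sit next to each other and differ, and Section 5.1.3.2 speaks of a fetus in utero, not of exposure through the father. The documents cannot settle this, since they refer to the Investigator's Brochure for the underlying data. If it is deliberate, though, exclusion 14 applies a longer date to men without explanation and is the text to change.

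Third, exclusion 14 is an entry test and inclusion 2 an undertaking about conduct, so their windows could legitimately differ. That is fair as to function. Both still concern reproductive risk from treatment, and no reason is given for different end dates.

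Finally, the consent form was not available and may already use the later date. In that case the protocol should be brought into line with it.

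**Conclusion.** The inconsistency is real. For a man whose last dose is pembrolizumab, inclusion 2 shortens the post-treatment period day for day with the gap between the two drugs, and removes it from 120 days. In the average-length example he keeps 35 of 120 days; the day-84 lenvatinib stop behind that figure is assumed.

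Its reach is small: only men who stop lenvatinib first and who have a partner of childbearing potential or might donate sperm. The documents do not give their number; zero to a few of 30 is plausible. Harm from a father's exposure to pembrolizumab is not shown, so this is a precaution. It should be corrected because men and site staff need a single stop date and the correction is cheap. Confidence is medium, mainly because the lenvatinib-only anchor could be intended.

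**What to change.** Reword inclusion 2 so that contraception and the bar on sperm donation both run through treatment and until at least 120 days after the final dose of pembrolizumab or lenvatinib, whichever is later. This restores 120 days for every gap and agrees with 3b and exclusion 14. Use the same wording in the consent form.

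If the sponsor confirms that lenvatinib-only is meant for men, leave inclusion 2 alone and narrow exclusion 14 for men to the same end date.

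As a clerical matter, correct the Appendix 3 reference from 5.11 to 5.1.1 if the source document also reads that way.

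The cost is a one-line amendment and matching consent text, with no added procedures. The downside is up to 120 extra days of contraception without sperm donation for a few men.
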